8.4. Deaths

If a patient dies, all relevant information will be discussed in the patient's narratives included in CSR.

8.5. Clinical Laboratory Test

All laboratory tests will be presented in SI units. By-visit summaries for chemistry and hematology laboratory tests including actual values and changes from baseline to each visit will be summarized using descriptive statistics. Shifts (below, within, and above the normal range) from baseline to each visit will be summarized using descriptive statistics. In order to calculate the percentages for the shifts summary, the total number of patients with available laboratory test results at baseline and at the post baseline visit will be used as the denominator for each relevant laboratory test and time point.

The incidence of abnormal values (below or above normal range) and the incidence of potentially clinically significant abnormal values (PCSA) (according to criteria specified in [Table 3](#)) will be summarized for laboratory data using descriptive statistics. The denominator for calculating the percentage of patients with at least 1 abnormality/PCSA for the group of chemistry/hematology tests will be the number of patients with both baseline and post baseline

laboratory result for at least 1 of the chemistry/hematology tests in that group. The denominator for calculating the percentage of patients with at least 1 abnormality/PCSA for each separate test will be the number of patients with both baseline and post baseline result for that test.

In addition, shift analysis from baseline to any time during the study for abnormal values as well as for PCSA values will be summarized using descriptive statistics. The shift categories for abnormal values will be presented as following: from below/within normal range at baseline to above normal range during the study, from above/within normal range at baseline to below normal range during the study, and condition not changed/changed to normal range value. The shift categories for PCSA values will be presented as following: from low/non PCSA value at baseline to high PCSA value during the study, from high/ non PCSA value at baseline to low PCSA value during the study, and condition not changed/changed to non PCSA value. In addition shift analysis for PCSA will also be presented as shift from normal baseline values to PCSA any time during the study following baseline. The denominator for calculating the percentages of patients will be the number of patients with both baseline and post baseline measurements for a specific test.

Table 3: Criteria for Potentially Clinically Significant Laboratory Values

Test	Criterion value
Serum chemistry	
Sodium	≤ 130 mmol/L ≥ 150 mmol/L
Potassium	≤ 3.2 mmol/L ≥ 5.5 mmol/L
Calcium	≤ 1.87 mmol/L ≥ 2.75 mmol/L
Phosphate	≤ 0.65 mmol/L ≥ 1.61 mmol/L
Glucose	≤ 3 mmol/L ≥ 13.88 mmol/L
Blood Urea Nitrogen	≥ 11.16 mmol/L
Alanine aminotransferase (ALT)	≥ 3 x ULN
Aspartate aminotransferase (AST)	≥ 3 x ULN
Alkaline phosphatase	≥ 3 x ULN
Gammaglutamyl Transpeptidase (GGT)	≥ 3 x ULN
Creatine phosphokinase (CPK)	≥ 3 x ULN
Creatinine	≥ 177 μ mol/L
Bilirubin (total)	≥ 28 μ mol/L
Albumin	≤ 25 g/L

Table 3: Criteria for Potentially Clinically Significant Laboratory Values (Continued)

Test	Criterion value
C Reactive Protein	$\geq 3x$ ULN
Amylase, Pancreatic	$\geq 3x$ ULN
Hematology	
Hemoglobin Men	≤ 11.5 g/dL ≥ 20 g/dL
Women	≤ 10 g/dL ≥ 18.5 g/dL
Leukocytes	$\leq 2.5 \times 10^9/L$ $\geq 21 \times 10^9/L$
Neutrophils	$\leq 1.49 \times 10^9/L$
Platelets	$\leq 100 \times 10^9/L$ $\geq 600 \times 10^9/L$
Fibrinogen	$\geq 1.5x$ ULN

ULN=upper limit of normal range.

Boxplots for all hematology tests, Fibrinogen, CRP and P-Amylase will be presented over time, including baseline, and all scheduled visits. Data recorded during unscheduled visits will not be included in the box plots.

In addition, for patients with a confirmed hemoglobin decrease of more than 1 g/dL who completed at least one of the tests in the anemia panel following baseline visit, data from the anemia panel/B12 tests and change from baseline will be presented using descriptive statistics.

Moreover, shift analysis of Common Terminology Criteria for Adverse Events (CTCAE) grade from baseline to any time during the study for Hemoglobin test will be presented using descriptive statistics. Grades of CTCAE will be defined according to CTCAE, v4 and are presented in [Table 4](#). For the cases with normal hemoglobin value, the CTCAE grade will be assigned zero. The denominator for calculating the percentages of patients will be the number of patients with both baseline and post baseline Hemoglobin measurements.

Table 4: Common Terminology Criteria for Adverse Events for Hemoglobin, v4

Grade	Description
1	LLN - 10.0
2	10.0 - 8.0 g/dL
3	<8.0 g/dL
4	Life-threatening consequences; urgent intervention indicated
5	Death

Also, a graph for the evaluation of drug-induced serious hepatotoxicity (eDISH) will be presented. The following steps should be performed in order to construct this graph:

1. For each patient in the ST population, find maximal post baseline value for ALT. If the same maximal value occurs in two separate visits, then the earlier visit value should be taken into account. Following that find the maximal Bilirubin(Total) value occurring after (or same day) the maximum ALT measurement occurred.
2. The maximal values identified in step 1 then should be divided by the ULN for each test accordingly.
3. Values received in step 2 will be presented in the scatter plot with ALT values on the x-axis and Bilirubin values on the y-axis. Two reference lines indicating extreme limits of 3 X ULN for ALT and 2 X ULN for Bilirubin will be shown as well.

Maximal values of AST, ALT and GGT at any time after randomization in terms of the upper normal range multiples will be provided in a separate table for patients with normal AST, ALT and GGT at baseline using descriptive statistics. The following intervals for maximal values will be used for this table: <= 1xULN, > 1xULN and <= 3xULN, > 3xULN and <= 5xULN, > 5xULN and <= 8xULN, > 8xULN. The denominator for calculating percentages will be the number of patients with post baseline hematology tests.

All analyses presented in the section will be repeated to include both part A and part B when the study is completed.

Listings for clinically significant abnormal laboratory data will be presented.

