## AMENDMENT HISTORY

The protocol for study TV5600-CNS-20006 (ARPEGGIO) (original protocol dated 21 July 2014) has been amended and reissued as follows:

Global Amendment 02	01 February 2016 301 patients enrolled to date
Global Amendment 01	01 July 2015 49 patients enrolled to date

Details about the changes and rationale for each change are provided in Section [17](#).

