### **3. STUDY DESIGN**

#### **3.1. General Design and Study Schema**

This is a multinational, multicenter, randomized, double-blind, parallel-group, placebo-controlled study, to evaluate the efficacy, safety and tolerability of daily oral administration of laquinimod (0.6 or 1.5 mg) in patients with PPMS.

Prior to 01 January 2016, eligible patients were randomized in a 1:1:1 ratio into 1 of the following treatment arms (a total of 286 patients were randomized 1:1:1 prior to 01 January 2016):

- Laquinimod 0.6 mg daily
- Laquinimod 1.5 mg daily
- Daily placebo

As of 01 January 2016, following a decision to discontinue the laquinimod 1.5 mg dose arm, additional eligible patients who are enrolled will be randomized in a 1:1 ratio into one of the following treatment arms:

- Laquinimod 0.6 mg daily
- Daily placebo

A capped randomization procedure will be employed to ensure that the proportion of EDSS 6.0 and 6.5 patients will not exceed more than 20% of all enrolled patients.

The study will include screening up to 6 weeks and 2 parts: Part A (core study) and Part B (data analysis).

Part A will last at least 48 weeks, and individual patients will experience variable treatment durations, depending on the order of enrollment.

[figure not shown]
Once the last ongoing patient completes the week 48 visit, the sponsor will declare end of Part A and begin performing study analyses.

In Part B, patients will continue their randomly-assigned blinded treatments with visits every 12 weeks until the completion visit. After up to approximately 24 weeks of Part B, or once data analysis has been completed and the design of a potential extension study has been finalized (including blinded or open-label treatment allocation), patients will be invited to the clinic for the completion visit and will be offered the opportunity to continue into an extension study, if applicable.

Patients will have the following study visits: screening visit (-6 weeks), baseline visit (week 0), weeks 4, 8, 12, 24, 36, 48, and every 12 weeks until study completion or early termination (ET).

The study schema is presented in [Figure 1](#) (prior to 01 January 2016) and [Figure 2](#) (from 01 January 2016).

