#### **7.3.1. Serum Chemistry**

The following serum chemistry tests will be performed at all study visits (except where stated):

- electrolytes
- fibrinogen
- glucose
- urea
- creatinine (Note: GFR will be estimated at all visits)
- ALT
- AST
- GGT
- alkaline phosphatase
- CPK

- in case of CPK results >ULN, creatine kinase MB isoenzyme (CK-MB) and troponin will be tested by the central laboratory.
- in case of CPK >10×ULN, an unscheduled visit to assess urine myoglobin will be required. The following blood tests will be repeated at the unscheduled visit: CPK, blood urea nitrogen, creatinine, electrolytes including potassium, calcium, phosphate.
- CRP
- pancreatic amylase
  - lipase will be tested in case of abnormal pancreatic amylase results
- total protein
- albumin
- direct and total bilirubin
- fasting lipid profile at weeks 0 and 48 and every 48 weeks until completion/ET.
- TSH, T3, and T4 at weeks 0 and 24 and every 24 weeks until completion/ET.
- Coagulation profile (prothrombin time [PT], activated partial thromboplastin time [aPTT] and INR), to be tested only if required according to Guidance on Safety Monitoring (see [Appendix B](#)).

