### 7.3.4. Urgent Safety Laboratory Panel

Unscheduled urgent safety laboratory samples may be collected at the discretion of the investigator or medical monitor at any time to assist with further investigations of cardiovascular events or other clinical event of interest. The samples should be collected as soon as possible in association with the event.

The following tests will be performed on these samples:

- serum chemistry panel (see Section 7.3.1)
- CBC panel (see Section 7.3.2)
- CK-MB
- troponin

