
 
• Brief Visuospatial Memory Test – Revised (BVMT-R) (first 3 recall trials): this requires the patient to inspect a <math>2 \times 3</math> stimulus array of abstract geometric figures (Form 1 from the Recall Stimulus Booklet). There are 3 learning trials of 10 seconds. The array is removed and the patient is required to draw the array from memory, with the correct shapes
 
	
 
• Brief Visuospatial Memory Test – Revised (BVMT-R) (first 3 recall trials): this requires the patient to inspect a <math>2 \times 3</math> stimulus array of abstract geometric figures (Form 1 from the Recall Stimulus Booklet). There are 3 learning trials of 10 seconds. The array is removed and the patient is required to draw the array from memory, with the correct shapes
 
	Details of scoring added

Original text with changes shown	New wording	Reason/Justification for change
in the correct position. Scoring of the BVMT-R drawings will be performed by a central expert vendor.	in the correct position. Scoring of the BVMT-R drawings will be performed by a central expert vendor.	
7.1.6. Protocol Defined Adverse Events for Expedited Reporting		
<del>No protocol defined adverse events for expedited reporting were identified for this study.</del> <del>Ischemic cardiac events (such as myocardial infarction, unstable angina, acute coronary syndrome etc), and cerebrovascular events (such as cerebral arterial occlusion, cerebral ischemia, etc) should be reported to the sponsor within 48 hours, including completion of the corresponding dedicated CRF.</del>	Ischemic cardiac events (such as myocardial infarction, unstable angina, acute coronary syndrome etc), and cerebrovascular events (such as cerebral arterial occlusion, cerebral ischemia, etc) should be reported to the sponsor within 48 hours, including completion of the corresponding dedicated CRF.	Due to cardiovascular findings at higher dose levels, adverse events for expedited reporting have been identified.
7.3.1. Serum Chemistry		
– in case of CPK results >ULN, creatine kinase MB isoenzyme (CK-MB) and troponin will be tested by the central laboratory.	– in case of CPK results >ULN, creatine kinase MB isoenzyme (CK-MB) and troponin will be tested by the central laboratory.	Troponin added (in case of CPK >ULN) to give additional cardiovascular assessment.

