7.3.4. Urgent Safety Laboratory Panel (Other sections affected by change: 3.11. Study Procedures)		
(new section)	Unscheduled urgent safety laboratory samples may be collected at the discretion of the investigator or medical monitor at any time to assist with further investigations of cardiovascular events or other clinical event of interest. The samples should be collected as soon as possible in association with the event. The following tests will be performed on these samples: 
 
• serum chemistry panel (see Section 7.3.1)
 
• CBC panel (see Section 7.3.2)
 
• CK-MB
 
• troponin
 
	Unscheduled laboratory test samples may be collected to allow further investigation of events of interest.
7.4. Vital Signs and Weight (Other sections affected by change: 3.11. Study Procedures)		
(new text)	Weight will be measured at all visits.	Weight will be used in association with GFR estimation, so needs to be measured at each visit.
7.7. Glomerular Filtration Rate Estimation (Other sections affected by change: 7.3.1. Serum Chemistry, 3.11. Study Procedures)		
Significant changes in laquinimod exposure, in particular in terms	Significant changes in laquinimod exposure, in particular in terms	Extra GFR monitoring

Original text with changes shown	New wording	Reason/Justification for change

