3. STUDY DESIGN

3.1. General Design and Study Schema

This is a multinational, multicenter, randomized, double-blind, parallel-group, placebo-controlled study, to evaluate the efficacy, safety and tolerability of daily oral administration of laquinimod (0.6 or 1.5 mg) in patients with PPMS.

On 30 December 2015 the Data Monitoring Committee (DMC) for the CONCERTO and ARPEGGIO studies held an unscheduled meeting to review cardiovascular events. The DMC found an imbalance in serious cardiovascular events in the high dose treatment arms (1.2 mg in CONCERTO, 1.5 mg in ARPEGGIO): in CONCERTO there were 6 such cases in the 1.2 mg arm but none in the 0.6 mg or placebo arms, along with a myocardial infarction in the ARPEGGIO 1.5 mg dose group and a cerebral infarction in a 31-year old patient in the 1.2 mg arm of CONCERTO. Due to these events and the DMC recommendation to stop all laquinimod treatment arms above 0.6 mg in the MS trials, the 1.5 mg treatment arm in the ARPEGGIO study was discontinued as of 01 January 2016.

Prior to 01 January 2016, eligible patients were randomized in a 1:1:1 ratio into 1 of the following treatment arms:

1. Laquinimod 0.6 mg daily
2. Laquinimod 1.5 mg daily- in total 95 patients were randomized to this arm.
3. Daily placebo

As of 01 January 2016, following a decision to discontinue the laquinimod 1.5 mg dose arm, additional eligible patients who are enrolled will be randomized in a 1:1 ratio into one of the following treatment arms:

1. Laquinimod 0.6 mg daily
2. Daily placebo

A capped randomization procedure will be employed to ensure that the proportion of Expanded Disability Status Scale (EDSS) 6.0 and 6.5 patients will not exceed more than 20% of all enrolled patients.

The study will include screening up to 6 weeks and 2 parts: Part A (core study) and Part B (data analysis).

Part A will last at least 48 weeks, and individual patients will experience variable treatment durations, depending on the order of enrollment.

Once the last ongoing patient completes the week 48 visit, the sponsor will declare end of Part A and begin performing study analyses.

[figure not shown]

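### If SAP 8.5's baseline requirement covers the triggered tests troponin and CK-MB, a first elevation on treatment without a baseline test drops out of the by-arm tables

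*SAP*

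**What the plan says.** **When the markers are measured.** Protocol 7.3.1 schedules CPK at all visits and adds that "in case of CPK results >ULN, creatine kinase MB isoenzyme (CK-MB) and troponin will be tested by the central laboratory". Protocol 7.3.4 gives a second route: "Unscheduled urgent safety laboratory samples may be collected at the discretion of the investigator or medical monitor". That panel includes both markers. Neither marker is in the scheduled safety panel defined in the footnotes to Protocol Tables 5 and 6.

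**When troponin began.** Table 7 of the protocol records the reflex test as new in Global Amendment 02: "Troponin added (in case of CPK >ULN) to give additional cardiovascular assessment". The urgent panel is a new section in the same amendment, with the reason "Unscheduled laboratory test samples may be collected to allow further investigation of events of interest". The CK-MB reflex test was already in place. The Amendment History dates Amendment 02 to 01 February 2016 and reports "301 patients enrolled to date".

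**How laboratory data are summarised.** SAP 5.2 defines baseline as the last value on or before the first dose. SAP 8.5 states that the denominator for the percentage of patients with an abnormal or potentially clinically significant value "for each separate test will be the number of patients with both baseline and post baseline result for that test". The any-time shift tables carry the same condition. SAP 5.1 allows unscheduled post-baseline values into the abnormal-value summaries. SAP Table 3 has no criterion for troponin or CK-MB, and the SAP text mentions neither.

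**The concern.** A baseline requirement suits a test that everyone has before dosing. It suits a triggered test badly. The patient of most interest is the one whose marker is measured, and found raised, for the first time on treatment. Without a pre-dose trigger that patient has no baseline result, so the per-test rule excludes them.

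The marker matters because of how it came into the study. Serious cardiovascular events, mainly myocardial infarction, closed the higher-dose arms of this trial and its sister trial. The DMC wanted long-term monitoring of 0.6 mg (Protocol 1.1.1.2), and reflex troponin was added within weeks. At stake is whether the data collected for that purpose reach a by-arm summary, including raised values that nobody reported as an adverse event.

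**Working it through.** **1. Reproduce the planned size of the continuing arms.** Protocol 9.2 gives a difference of 0.3, an SD of 0.8, two-sided alpha of 5% and 126 per arm. A two-sample power calculation returns 84.5%, against the stated 84%. Inflating for 10% dropout: 252 / 0.9 = 280. Also 375 − 95 = 280, or 140 per arm as in SAP 3.3. The 95 is consistent with 1:1:1 allocation: 286 / 3 = 95.3.

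**2. Continuing-arm patients enrolled before troponin entered the protocol.** The inputs are 301 enrolled at Amendment 02 (Amendment History) and, for the 1.5 mg arm, "in total 95 patients were randomized to this arm" (SAP 3.1). That arm closed on 01 January 2016, so all 95 are among the 301.
- 301 − 95 = 206
- Cross-check from Protocol 3.1, "a total of 286 patients were randomized 1:1:1 prior to 01 January 2016": 286 − 95 = 191; 301 − 286 = 15; 191 + 15 = 206

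These 206 can have a troponin on treatment but no protocol baseline: 206 / 280 = 73.6%.

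**3. Ceiling on the troponin denominator.**
- 375 − 301 = 74, and 280 − 206 = 74
- 74 / 280 = 26.4%, or 74 / 2 = 37 per arm

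**4. Sensitivity of the ceiling.** The 375 is approximate, and enrolled is read as randomised.
- Counting from the 286 randomised before 01 January 2016: 375 − 286 = 89; 89 / 280 = 31.8%
- Total of 360: 59 / 265 = 22.3%
- Total of 390: 89 / 295 = 30.2%

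**5. Below the ceiling.** Each of the 74 also needs a trigger before first dose, in practice CPK above ULN, and then a further trigger after baseline. The documents do not give the share with a pre-dose trigger. Assuming 5% to 50%:
- 74 × 0.05 = 3.7 patients, 1.3% of 280
- 74 × 0.50 = 37 patients, 13.2% of 280

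**6. The 1.5 mg arm.** Dosing stopped as of 01 January 2016. SAP 5.1 counts data up to seven days after last dose as on treatment. Amendment 02 is dated 01 February 2016. By these dates, 0 of the 95 can have an on-treatment protocol troponin.

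**7. CK-MB.** Its reflex test pre-dates Amendment 02, so the ceiling of 74 does not apply. Its baseline coverage depends only on how many patients had a trigger before dosing, which the documents do not give. No estimate is made.

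**8. Other planned by-arm output.** Table 15.92 shows actual chemistry values by visit and needs no baseline, so reflex results from scheduled visits could appear there with n and maximum. By-visit summaries cover scheduled and early termination visits (SAP 5.1), so unscheduled draws are not included, and the table does not count patients ever raised. The row for at least one abnormal chemistry test needs only one test with both results, but it does not identify the marker. Listing 16.2.8.02 would hold individual chemistry values and is not a summary.

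**The case against.** The strongest objection is that SAP 8.5 may not govern these tests at all. The SAP never names them, Table 3 omits them, and Protocol 7.3.4 lists them as items separate from the serum chemistry panel. Only their position under CPK in Protocol 7.3.1 places them in serum chemistry. This stands as a limit on confidence, but it does not close the gap. Outside the chemistry tables, the markers have no by-arm table.

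A second objection is that the cardiac question is covered elsewhere. CPK is measured at every visit, has a Table 3 criterion and is tabulated by arm on nearly full denominators. Laboratory abnormalities that are clinically significant or need work-up become adverse events (Protocol 7.1.1). Ischemic cardiac and cerebrovascular events are reported within 48 hours on a dedicated form (Protocol 7.1.6), and an independent DMC reviews safety data regularly (Protocol 7). All of this stands. A reader might infer that a cardiac signal at 0.6 mg could go unseen; the documents do not support that. What remains is elevations that nobody judged significant and that prompted no work-up, plus the marker summary itself.

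A third objection is that the incompleteness comes from triggered testing, which no denominator can cure, and that both continuing arms share the same triggers and timing. That is also right. No between-arm bias is claimed, and the remedy below yields counts, not rates.

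A reader might also infer that a patient without a baseline would be counted over a tiny denominator and print as a grossly inflated percentage. The SAP gives no such instruction. The ordinary reading takes the numerator from within the denominator, so the consequence is omission.

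Nor should the SAP's own test-specific rules be pressed as precedents. The anemia panel has a scheduled baseline in everyone, and the eDISH plot uses tests drawn at every visit. They show that SAP 8.5 can carry a special rule, not that it has already waived a baseline for a triggered test.

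**Conclusion.** The point holds in a limited form and is worth a small change. If troponin is handled as chemistry, at least about 206 of the planned 280 continuing-arm patients (74%) cannot enter its per-test denominator. At most about 74 (26%; 32% on the loosest count) can, and only with a trigger before first dose. First elevations on treatment in patients without a baseline test are then missing from the by-arm abnormal and any-time shift tables. If the markers are not handled as chemistry, those tables do not exist for them. The same logic applies to CK-MB, with its size unknown.

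The figures assume that the planned 375 is reached and that the Amendment 02 date is the effective start of troponin testing. Confidence is moderate, because the application of SAP 8.5 is inferred. The primary and secondary analyses and the capture of clinical cardiac events are unaffected.

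**What to change.** In SAP 8.5, exempt troponin and CK-MB from the baseline requirement and add one descriptive table, by arm for 0.6 mg and placebo. For each marker, show three numbers together: safety-population patients with any on-treatment post-baseline value above ULN (scheduled or unscheduled), patients tested after baseline, and all patients in the safety population. Table 3 need not change, since the existing above-normal category serves. Footnote that testing is triggered and that troponin testing began partway through enrolment.

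The cost is a few lines of SAP text and one table from data already collected, with no new testing and no effect on alpha. The downside is selection: patients are tested because CPK was raised or an event was suspected, and untested patients are not known to be normal. The counts are therefore descriptive, and neither denominator gives a reliable rate.

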**Table 3: Tabulated List of Adverse Reactions**

Cardiac disorders	
Uncommon:	Myocardial infarction
Infections and infestations	
Common:	Urinary tract infection, skin infections
Uncommon:	Appendicitis, furuncle
Blood and lymphatic system disorders	
Very Common:	Decreased platelets, increased white blood cells
Common:	Anemia a
Psychiatric disorders	
Common:	Anxiety
Nervous system disorders	
Very Common:	Headache
Rare	Cerebrovascular accident
Respiratory, thoracic and mediastinal disorders	
Common:	Cough, bronchospasm
Uncommon:	Asthma
Gastrointestinal disorders	
Very Common:	Abdominal pain
Common:	Constipation, toothache, abdominal distension, nausea, and vomiting
Uncommon:	Dry mouth
Hepatobiliary disorders	
Common:	Liver enzymes increased a (alanine aminotransferase [ALT], aspartate aminotransferase [AST], gamma-glutamyl transpeptidase [GGT])
Musculoskeletal and connective tissue disorders	
Very Common:	Back and neck pain
Common:	Arthralgia
Uncommon:	Bursitis
Reproductive system and breast disorders	
Common:	Menstruation disorders and uterine bleeding
General disorders and administration site conditions	
Common:	Peripheral edema
Investigations	
Common:	Blood fibrinogen increased, blood amylase increased, creatinine decreased, blood C-reactive protein increased b
Renal and urinary disorders	
Uncommon:	Micturition urgency

a For liver enzyme elevations and anemia - see below.

b Blood C-reactive protein increased was observed at doses higher than 0.6 mg.

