### **3.6.5. Renal Impairment**

To avoid exposures to higher levels of laquinimod (see Section 1.3.2.1), a stopping rule related to renal impairment has been introduced. Patients who develop renal disease associated with moderate or severe functional impairment, defined as glomerular filtration rate (GFR)  $\leq 60$  mL/min/1.73 m^2, while participating in the study should stop study medication temporarily and the GFR assessment should be repeated. If the renal impairment is confirmed (GFR  $\leq 60$  mL/min/1.73 m^2), the patient should stop study medication permanently.

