## **7.7. Glomerular Filtration Rate Estimation**

Significant changes in laquinimod exposure, in particular in terms of unbound drug fraction, are predicted in patients with moderate and severe renal impairment (see Section 1.3.2.1). Consequently, GFR will be estimated at all visits to monitor renal function in the study in order to identify patients with potentially impaired laquinimod clearance. Patients with a confirmed GFR  $\leq 60$  mL/min/1.73 m^2 should stop study medication temporarily and the GFR assessment should be repeated. If the renal impairment is confirmed (GFR  $\leq 60$  mL/min/1.73 m^2), the patient should stop study medication permanently (see Section 3.6.5).

Following recent findings connecting Gd-based contrast agents and nephrogenic systemic sclerosis, the GFR result should be available prior to the baseline MRI scan. GFR estimation will be done in accordance with the central laboratory creatinine value measurement performed at the screening visit. The central laboratory will report estimated GFR; however, if the result is not available prior to the baseline MRI scan, the CKD-EPI Creatinine Equation (2009) from the following online GFR calculator should be used by the investigator:

[http://www.kidney.org/professionals/kdoqi/gfr\\_calculator.cfm](http://www.kidney.org/professionals/kdoqi/gfr_calculator.cfm)

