9. PHARMACOKINETIC ANALYSIS

A single blood sample will be collected from all patients at weeks 4, 8, 12, 24 and 48. Pharmacokinetics of laquinimod will be evaluated using a PPK approach. The effect of covariates on the pharmacokinetics of laquinimod will be evaluated. Possible covariates will include demographic variables (eg, age, gender, body weight and ethnicity), clinical variables, concomitant medications, blood and urine chemistry variables and markers of renal function (creatinine clearance and serum creatinine).

This analysis will be reported in a separate PPK report.

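### The SAP names no output counting patients at the protocol's renal stopping limit (GFR of 60 or less), and its creatinine flag of 177 umol/L lies well beyond that limit

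*SAP*

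**What the plan says.** Protocol Section 7.7 gives the purpose of the monitoring: "GFR will be estimated at all visits to monitor renal function in the study in order to identify patients with potentially impaired laquinimod clearance". Section 3.6.5 attaches a rule to it. At GFR of 60 mL/min/1.73 m2 or less the patient "should stop study medication temporarily and the GFR assessment should be repeated"; if the low value is confirmed, "the patient should stop study medication permanently". The reason is exposure. Section 1.3.2.1 reports a 1.4-fold increase observed in moderate renal impairment and predicts a 1.65-fold increase in unbound drug. Section 9.8.2 says that laboratory values will all be compared with prespecified boundaries and the potentially clinically significant ones listed.

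The SAP was written with this amendment in hand (its Preface lists it), and the footnotes to its visit schedules (SAP Tables 1 and 2) repeat the GFR rule. The boundaries are in Section 8.5, "Table 3: Criteria for Potentially Clinically Significant Laboratory Values". The renal entries there are creatinine of at least 177 umol/L and urea nitrogen of at least 11.16 mmol/L. There is no GFR entry. Section 8.5 describes no GFR summary or shift, Section 13 lists no GFR table, listing or graph, and Section 12 does not record this as a change from the protocol.

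**The concern.** A safety stop was created for this trial, with a numerical limit measured at every visit, but the analysis plan sets no boundary at that limit. The hepatic rule is treated differently. Protocol Section 3.6.2 acts at 3, 5 and 8 times the upper limit of normal for ALT and AST, and the SAP follows with a flag at 3 times, a plot of peak ALT against bilirubin, and bands of maximal values cut at 3, 5 and 8 times. The renal rule has no counterpart.

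If the creatinine flag sits well beyond the GFR limit, the tables of potentially clinically significant values can miss patients whose drug was stopped for renal impairment. The report then need not show how many patients in each arm met the rule, which is the first thing a reader would ask of the added monitoring.

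**Working it through.** The plan states no figure that links the two limits, so there is nothing to reproduce. The check converts one limit into the scale of the other.

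**Inputs from the documents**
- SAP Section 8.5, Table 3: creatinine flag at 177 umol/L.
- Protocol Section 3.6.5: GFR limit of 60.
- Protocol Section 4.1: age 25 to 55.
- Protocol Section 7.7: CKD-EPI creatinine equation (2009), named only as the investigator's fallback when the central laboratory's GFR is not available before the baseline MRI. The central laboratory's own equation is not stated.

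**Assumed**
- The standard CKD-EPI 2009 coefficients and 88.4 umol/L per mg/dL; the documents give neither.

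**Formula.** For creatinine S (mg/dL) above k:

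GFR = 141 x (S/k)^-1.209 x 0.993^age x (1.018 if female) x (1.159 with the race factor), with k = 0.9 for men and 0.7 for women.

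Solved for creatinine at GFR 60:

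S = k x (141 x 0.993^age x factors / 60)^(1/1.209).

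**Worked cells**
- 177 umol/L is 177/88.4 = 2.002 mg/dL.
- Man aged 25: 141 x (2.002/0.9)^-1.209 x 0.993^25 = 45.0.
- Woman aged 55: 141 x 1.018 x (2.002/0.7)^-1.209 x 0.993^55 = 27.4.

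| | GFR at creatinine 177 | Creatinine at GFR 60 (umol/L) | With race factor: GFR at 177 | With race factor: creatinine at GFR 60 |
|---|---|---|---|---|
| Man, 25 | 45.0 | 139.5 | 52.1 | 157.6 |
| Man, 55 | 36.4 | 117.2 | 42.2 | 132.4 |
| Woman, 25 | 33.8 | 110.1 | 39.2 | 124.4 |
| Woman, 55 | 27.4 | 92.5 | 31.7 | 104.5 |

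In every cell the stopping limit is reached before the creatinine flag. A woman of 55 at the limit would need her creatinine to rise by a further factor of 177/92.5 = 1.91 to be flagged. For a man of 25 with the race factor, the narrowest case, it is 177/157.6 = 1.12.

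**Analysis window.** SAP Section 5.1 excludes non-MRI measurements taken more than seven days after the last dose. The renal rule stops the drug first and repeats GFR afterwards, and Section 3.6.5 sets no interval for the repeat. If the patient does not restart, a confirmatory value taken on day 8 or later falls outside the analysed data. Even a new GFR row would miss it unless the window is addressed.

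**The case against.** The strongest reply is that the SAP is not blind to these patients.

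- Urea nitrogen is a second renal flag, so creatinine is not the only route into the table.
- Section 8.5 also summarises creatinine by visit, any value outside the normal range, and shifts to above normal (tables 15.92, 15.94, 15.96 and 15.100). None of these uses the 177 cut-off.
- Protocol Section 7.1.1 makes a laboratory abnormality an adverse event if it leads to withdrawal or needs further work-up. Adverse events causing discontinuation are tabulated by arm (table 15.88).
- Protocol Section 7.3.1 mentions GFR under creatinine within serum chemistry, so the by-visit chemistry summaries could be read to include it.
- A limit meant to avoid excess exposure and a limit meant to screen for marked abnormality need not coincide.

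Much of this stands. A reader might infer that stopped patients go uncounted, or that the laboratory tables would show no renal signal. The documents support neither: some patients will surface by these routes, and whether creatinine at GFR 60 exceeds normal depends on reference ranges that are not given. What the reply does not supply is a count at the protocol's limit. Normal-range summaries use another boundary, a single creatinine cut-off cannot follow a limit that moves with age and sex, and the withdrawal reasons in protocol Section 4.3.1 contain no renal category.

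A further inference is tempting. The protocol's Table 3 of adverse reactions includes "creatinine decreased, blood C-reactive protein increased", and SAP Section 9 offers creatinine clearance and serum creatinine as possible covariates in the population pharmacokinetic model. One might conclude that the model is biased, or that estimated GFR reads too high on drug. Neither is established: the documents do not say whether baseline or on-treatment values would be used, and they give the frequency of the creatinine decrease but not its size.

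**Conclusion.** The point holds as a gap in safety reporting. The missing GFR criterion is certain, and no output named in the SAP counts patients at GFR of 60 or less. Patients stopped under the renal rule need not appear in the tables of potentially clinically significant values; that is weaker than saying they never do.

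The size rests on the assumed CKD-EPI 2009 coefficients and on the central laboratory using that equation or a similar one. On that basis the creatinine flag corresponds to GFR of about 27-45 (up to 52 with the race factor), against a limit of 60. The direction is the same in every age, sex and race-factor cell calculated. How many patients this affects cannot be derived from the documents. No efficacy inference is touched, and nothing here bears on whether either limit is clinically right.

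**What to change.** In the SAP:

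- Add GFR of 60 mL/min/1.73 m2 or less, the protocol's own figure, to Table 3 of Section 8.5 as an analysis category.
- Summarise GFR and its change from baseline by visit and arm.
- Report by arm the number of patients shifting from above 60 to 60 or less, at first occurrence and confirmed. Because exclusion criterion 26 bars GFR of 60 or less at screening, this shift should be easy to interpret.
- State in Section 5.1 or 8.5 that confirmatory GFR values count even when taken more than seven days after the last dose.
- Add the matching entries to Section 13.

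The cost is one row, one or two tables and a sentence on the window, all from data the protocol already collects. The downside is more flagged patients. The clinical stopping rule is left as it is.
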